9.4.8 Safety analyses

The safety evaluation will be based on the review of vital signs parameters and reported adverse events. The safety analysis will be conducted according to the sponsor's document "Analysis and reporting of safety data from Clinical Trials through the Clinical Study Report" (BTD-009536).

All the safety analyses will be performed using the safety population. When applicable, results will be by cohorts and overall.

9.4.8.1 Adverse events

9.4.8.1.1 Definitions

Adverse events will be coded to a "Preferred Term (PT)" and "High Level Group Term (HLGT)", "High Level Term (HLT)" and primary "System Organ Class (SOC)" using the Medical Dictionary for Regulatory Activities (MedDRA, version currently in use by the sponsor at the time of database lock).

For patients' cohort, they will be classified into predefined standard categories according to chronological criteria:

- Pre-treatment AEs: AEs that occurred, worsened or became serious during the pre-treatment period defined as the time between informed consent signature and the first IMP administration.

- Treatment emergent AEs (TEAEs): AEs that occurred, worsened or became serious during the TEAE period defined as the time from the first IMP administration up to the end of treatment visit (EoT included).
- Post-TEAEs: AEs that occurred, worsened or became serious during the post-TEAE period defined as the time starting after the TEAE period.

TEAEs will be assigned to the treatment received at the time of the AE onset.

If the onset date (or time) of an AE (occurrence, worsening or becoming serious) is incomplete or missing, then the AE will be considered as a TEAE unless a partial date (or time) shows it as a pre- or post-treatment event.

For all healthy volunteers, safety data will be considered as part of a single period starting with the signature of the informed consent and ending with the end of study visit (EoS included).

All AEs reported in the study will be listed, sorted by subject/patient, onset date and time.

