Lesional and non-lesional skin areas for TEWL assessment and STS will be identified on the upper limbs or lower limbs at baseline ("predefined skin area"). TEWL and STS-assessment at pre-defined non-lesional (normal looking) skin area in AD patients should be made about 4 cm from the edge of the lesional area.

Within the predefined lesional skin (LS) and non-lesional skin (non-LS) areas three closely adjacent spots will be identified for subsequent skin barrier function assessment (3 spots on lesional skin, 3 spots on non-lesional skin). These spots must not overlap with each other once skin tapes are applied.

The skin barrier function without and before STS will be assessed using TEWL measurement on each of the three spots within these pre-defined skin areas at each visit.

Repeated TEWL assessment in pre-defined lesional and non-lesional skin areas of AD patients after STS for lipidomics, proteomics and transcriptomics analysis in STS samples will be conducted at baseline (Week 0, Day 1), Week 2 (Day 15), Week 4 (Day 29), Week 8 (Day 57), Week, 12 (Day 85), and at EoT at Week 16 (Day 113).

In order to allow the skin to recover from the STS, the skin barrier function assessment with STS will be performed as follows: STS assessment on baseline (Week 0), Week 8 and Week 16 will be conducted on the first spot within the predefined lesional and non-lesional skin area. STS assessment on Week 2 will be conducted on the second spot. STS assessment on Week 4 and Week 12 will be conducted on the third spot.

TEWL will be measured before and after 5, 10, 15, and 20 STS (5 TEWL assessments per visit) on targeted, predefined lesional, non-lesional skin in AD patients at baseline, Week 2, Week 4, Week 8, Week 12, and Week 16 on the predefined first, second or third spot, respectively.

Skin barrier function in approximately twenty healthy volunteers matched for age, gender, location of targeted lesion area, and study site to the AD cases will be assessed in a similar manner at baseline, twice a week during the first two weeks, once a week during Week 3 to Week 4, every two weeks from Week 4 to Week 8, and every four weeks up to Week 16 thereafter, serving as a reference comparator for skin barrier function.

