- For AD patients aged ≥ 12 to < 18 years the dose regimen will be based on body weight on Day 1. No change in dosing will be made if body weight increases or decreases during the study. Dose allocation will be according to the following table:

Body Weight	Loading Dose on Day 1	Subsequent Doses (Q2W) ^a
less than 60 kg	400 mg (two 200 mg injections)	200 mg
60 kg or more	600 mg (two 300 mg injections)	300 mg

^a Every second week (Q2W)

- AD patients age 18 years and older will receive a SC loading dose of 600 mg on Day 1, followed by 300 mg Q2W SC through Week 14. Drug will be administered by study site staff at baseline, Week, 2, 4, 6, 8 and 12. Drug will be self-administered by AD patients at home at Week 10 and 14.

Post-trial access to study medication

- After the study is completed, patients will not be provided with any further study medication as part of this protocol.

Duration of study period (per participant)

Study participation for each patient and healthy volunteer will be a total of approximately 24 weeks including:

- Screening period: Up to 4 weeks from signed informed consent.
- Open label dupilumab treatment (AD patients) and observation period (healthy volunteers): 16 weeks from baseline on Day 1.
- Follow-up period: 4 weeks after the EOT visit at Week 16.

Statistical considerations: Analyses will be descriptive and explorative.

After all patients and healthy volunteers have completed the Week 16 assessments, the data up to this time will be cleaned, and locked; all endpoints relating to Week 16 will be analyzed and reported at this time.

- **Sample size calculations**
 - Sample size for this exploratory study was based on medical/clinical judgement and is consistent with the sample size from similar studies in the literature (1). No formal sample size calculation was performed. TEWL data collected in similar settings as planned for this study were not available: ie, TEWL values after 5 STS, and pre- and post-dupilumab treatment are unknown.
- **Analysis of primary, secondary and exploratory endpoints:**
 - This is an exploratory study. No formal statistical testing will be conducted.
 - Descriptive statistics will be generated by group, time point and type of skin area (lesional or non-lesional, if applicable) for selected parameters of interest. Raw data

and changes from baseline: ie, absolute and percent changes, for selected parameters will be summarized in descriptive statistics and summary plots.

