			D4 ±2 days	D8 ±2 days	D11 ±2 days	D15 ±2 days	D22 ±2 days	D29 ±2 days	D43 ±2 days	D57 ±3 days	D85 ±3 days				
Day	D-28 to D-1	D 1												UNSCH	
Week		W0	W1			W2	W3	W4	W6	W8	W12	W16	W20		
Visits	V01	V02	V03	V04	V05	V06	V07	V08	V09	V10	V11	V12	V13		
Quality of sleep NRS ^g		X	X	X	X	X	X	X	X	X	X	X		(X)	X
Safety															
Adverse event collection	X	X	X	X	X	X	X	X	X	X	X	X	X	X	X
Height		X													
Body weight		X										X			X
Vital signs ^d	X	X								X		X		(X)	X
Physical examination	X	X ^k										X ^k			X ^k
Pregnancy test (urine), WOCBP only ^e	X	X						X		X	X	X			
DNA sampling for filaggrin gene sequencing		X													
Optional assessments															
DNA sampling for future research		X													
Biomarker research samples (serum and plasma)		X										X			X

a EoS safety follow-up by phone.

b Loading dose dupilumab arm 600 mg (300 mg x 2 ie, two 300 mg syringes) for all adult patients and for those adolescents weighing 60 kg and above, and 400 mg (200 mg x 2 ie. two 200 mg syringes) for adolescent patients below 60 kg, followed by bi-weekly SC dosing of 300 mg dupilumab to adults and adolescents weighing 60 kg and above and bi-weekly SC dosing of 200 mg to adolescents weighing below 60 kg. Dupilumab administration on following days: D1 (V02,W0) baseline, D15±2days (V06, W2), D29±2days (V08, W4), D43±2days (V09, W6), D57±3days (V10, W8), D71±3days (W10; self-administration of dupilumab at home), D85±3days V11, W12), D99±3days (W14; self-administration of dupilumab at home).

c Assessments on treatment days are to be conducted before administration of dupilumab.

d Vital signs, including systolic and diastolic blood pressure (mmHg), pulse rate (beats per minute), body temperature (°C), and respiratory rate will be measured at Screening, Baseline at Week 0, Week 8, and Week 16 (EoT). Height (cm) will be measured at Baseline only. Body weight (kg) will be measured at Baseline, and Week 16 (EoT).

e Only for women of childbearing potential. Pregnancy will lead to definitive treatment discontinuation in all cases.

f DLQI will be used for adults; CDLQI will be used for adolescents.

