8.5 TREATMENT OF OVERDOSE

Sponsor does not recommend specific treatment for an overdose.

In the event of an overdose, the Investigator should:

1. Contact the Medical Monitor immediately.
2. Closely monitor the participant for any AE/SAE and laboratory abnormalities until dupilumab can no longer be detected systemically (at least 28 days).
3. Document appropriately in the CRF.

Decisions regarding dose interruptions or modifications will be made by the Investigator in consultation with the Medical Monitor based on the clinical evaluation of the participant.

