9.3 POPULATIONS FOR ANALYSES

For purposes of analysis, the following populations are defined ([Table 3](#)):

Table 3 - Populations for analyses

Population	Description
Enrolled	All participants who sign the ICF
Intent-to-treat (ITT)	The ITT population includes all enrolled patients, who received at least one dose of IMP and all enrolled healthy volunteers who have at least one TEWL/STS assessment performed, irrespective of compliance with the study protocol and procedures.
Modified Intent-to-treat (mITT)	The mITT population includes all ITT participants. If prohibited therapies for AD (see Section 6.5.1) are used and assessed by the study team as having a significant impact on skin barrier only visits prior to rescue treatment use are considered.
Efficacy	The mITT and ITT populations
Safety	The safety population includes all patients, who actually received at least one dose of IMP or had at least one TEWL/STS assessment and all healthy volunteers who have at least one TEWL/STS assessment performed.

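### For AD patients the TEAE and AESI rates stop at the EoT visit: no AESI rate covers the 4-week safety follow-up, the closing visit for early stoppers is not stated, and never-dosed patients can enter the denominator

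*Protocol*

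**What the plan says.** **Window.** Protocol Section 9.4.8.1.1 sets the TEAE period for AD patients as "the time from the first IMP administration up to the end of treatment visit (EoT included". Anything that starts, worsens or becomes serious later is a post-TEAE.

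**Schedule.** The last planned dose is at "D99±3days (W14; self-administration of dupilumab at home" (Section 1.3, footnote b). The synopsis places "EoT at Week 16 (Day 113", and Section 1.3 allows ±3 days. The synopsis then gives "Follow-up period: 4 weeks after the EOT visit at Week 16", and Section 1.3 describes that contact as "EoS safety follow-up by phone" at Day 141 ±3. AEs are collected up to and including it.

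**Tables.** Section 9.4.8.1.2 builds the overview and the SOC/PT tables from TEAEs only, for AD patients in the safety population, and gives AEs outside the window their own summary. Section 9.4.8.1.5 tabulates treatment-emergent AESIs only. All AEs are listed (9.4.8.1.1), and deaths and serious AEs are listed without a window (9.4.8.1.3).

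**Denominator.** Table 3 in Section 9.3 defines the safety population as "all patients, who actually received at least one dose of IMP or had at least one TEWL/STS assessment", plus the assessed volunteers.

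**SAP.** Section 1.2 adds AE summaries by cohort and age group, and Section 1.3 adds a rule for missing onset times. Neither changes the window or the safety population.

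**The concern.** The protocol plans a safety follow-up and collects AEs during it, but the rates most readers will quote stop before it begins. A keratitis starting on Day 120, 21 days after the last planned dose (120 − 99), would be missing from the AESI table and would appear only in the general summary of out-of-window AEs and in the listings.

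Two other provisions look further than 14 days past treatment. Exclusion criterion E 18 asks for contraception for 12 weeks after the last dose, and Section 6.5.1.1 asks for titer checks when a vaccination is needed within 16 weeks of stopping. These are precautions and do not fix a duration of drug effect, but they make a 14-day limit on what may count as treatment-emergent less than obvious.

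Two definitions are also loose. Section 1.3 has a separate column for a premature EoT visit, while Section 7.1.1 keeps patients who stop drug in follow-up to the scheduled end, and the TEAE definition does not say which visit it means. An AD patient with a Day 1 TEWL/STS assessment but no dose belongs to the safety population and yet cannot have a TEAE.

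**Working it through.** **Inputs.** First dose Day 1; last planned dose Day 99 ±3; EoT Day 113 ±3; EoS Day 141 ±3 (protocol Section 1.3). Exposure is last dose minus first dose plus 14 days (Section 9.4.5.1). About 24 AD patients are planned (Section 9.2).

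**1. The plan's own figures.** Follow-up after EoT: 141 − 113 = 28 days = 4 weeks, as stated. Planned exposure: 99 − 1 + 14 = 112 days. First dose to EoT: 113 − 1 = 112 days. The TEAE window and the exposure definition therefore agree for a patient who completes dosing.

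**2. Time counted and not counted.**

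| Interval | Nominal (days) | Shortest | Longest |
|---|---|---|---|
| Last dose to EoT | 113 − 99 = 14 | 110 − 102 = 8 | 116 − 96 = 20 |
| EoT to EoS | 141 − 113 = 28 | 138 − 116 = 22 | 144 − 110 = 34 |
| Last dose to EoS | 141 − 99 = 42 | 138 − 102 = 36 | 144 − 96 = 48 |

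Share of observation after first dose that lies outside the TEAE and AESI rates: 28 / (141 − 1) = 28/140 = 20%.

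**3. What that might mean in patients.** The documents give no AE rates, so this step rests on assumed 16-week risks p and a constant hazard. The 20-week risk is then 1 − (1 − p)^(140/112).

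| Assumed 16-week risk | 20-week risk | Expected patients of 24, 16 weeks | Expected patients of 24, 20 weeks | Difference |
|---|---|---|---|---|
| 5% | 6.2% | 1.20 | 1.49 | 0.3 |
| 10% | 12.3% | 2.40 | 2.96 | 0.6 |
| 20% | 24.3% | 4.80 | 5.84 | 1.0 |
| 40% | 47.2% | 9.60 | 11.33 | 1.7 |

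**4. Early stoppers.** Take a patient whose last dose is on Day 43 and whose premature EoT visit falls on Day 57 (an illustration). If that visit closes the window, 57 − 43 = 14 days count after the last dose. If the scheduled Week 16 visit closes it, 113 − 43 = 70 days count. The text allows either.

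**5. Denominator.** With 24 dosed patients and one assessed but undosed, k events give k/25 instead of k/24. The ratio is 24/25 = 0.96, a 4% relative reduction in every TEAE percentage. A true 20% would be shown as 0.20 × 0.96 = 19.2%.

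**The case against.** The strongest defense is that this is a disclosed, pre-specified choice in a small descriptive study. The window runs one dosing interval past the last planned dose and matches the exposure definition. A 16-week percentage answers a different question from a 20-week one and is not thereby biased. With about 24 AD patients, the listings can be read in full. Ascertainment also differs: 11 on-site visits from Day 1 to EoT, then a single phone call. All of this stands, and it argues for keeping the present tables. What it does not supply is an AESI rate for the follow-up, a rule for early stoppers, or a reason to divide treatment-emergent counts by patients who were never treated.

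An undosed patient in the safety population is unlikely, since the dose is planned at the same visit as the first TEWL assessment. Keeping such a patient in the safety population is defensible because tape stripping carries its own risks (Section 2.3.1). The point concerns only the TEAE percentages.

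Two stronger readings are tempting, and the documents support neither.

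- A reader might infer from Section 8.5, which asks for monitoring "until dupilumab can no longer be detected systemically (at least 28 days", that the protocol regards drug as detectable for 28 days after regular dosing. That sentence governs overdose only, and pharmacokinetics are not evaluated (Section 8.6). Even taken at face value, 99 + 28 = Day 127, which is not EoS.
- A reader might see an inconsistency in the volunteers' safety period "ending with the end of study visit (EoS included". Volunteers receive no drug, so they have no treatment-emergent period, and Section 9.4.8.1.2 gives them no TEAE summary.

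**Conclusion.** The point holds as a limited one about headline rates and definitions. For AD patients, 28 of 140 planned days after first dose (20%) lie outside the TEAE overview, the SOC/PT tables and the AESI table. AEs in those days are still summarized apart and listed, so the plan neither loses them nor contradicts itself. The real gaps are that no AESI rate covers the follow-up, that the closing visit for early stoppers is unstated, and that the denominator can include patients who cannot have the event.

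The size in events is unknown. Under the constant-hazard assumption, a table through EoS would gain about 0.3 to 1.7 patients in 24 for 16-week risks of 5% to 40%. The assumption may fail in either direction, because the event rate may change after treatment and one phone call may find fewer events. The 4% dilution applies only if one undosed patient is in fact included among 25. A reader might conclude that the planned rates are understated. The documents show only that they cannot exceed rates taken through EoS on the same patients.

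**What to change.** In the SAP:

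1. Keep the TEAE and AESI tables to EoT as planned.
2. Add AE and AESI summaries for AD patients from first dose through EoS, for completers and early stoppers alike, beside the current tables.
3. State whether the premature or the scheduled Week 16 EoT visit closes the TEAE window for patients who stop drug early.
4. Compute TEAE percentages on AD patients with at least one dose, and list any AD patient assessed but not dosed separately. The safety population itself can stay as it is.

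No new data are needed. The cost is a few extra tables, and those through EoS must follow the Week 20 calls and so come after the Week 16 lock described in the synopsis. The added burden is small, because the promised summary of out-of-window AEs and the full AE listing already need the follow-up data. Redefining the TEAE period itself to end at EoS is a debatable alternative: it would mix two levels of ascertainment and delay the main tables.

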9.4.8.1.2 Treatment-emergent adverse events

The following TEAEs summaries will be provided for the patients' cohort of the safety population:

Overview of TEAEs: number and percentage of subjects with any TEAE, any serious TEAE, any TEAE leading to death (if any occurred), any TEAE leading to permanent treatment discontinuation, and any TEAE of special interest.

- Summary of TEAEs by primary SOC and PT:
 - Number and percentage of patients with at least one TEAE;
 - Number of occurrences of TEAEs.

Patients presenting TEAEs will be listed sorted by primary SOC and PT. By definition, no TEAEs summary will be displayed for healthy volunteers.

AEs that occur outside the treatment emergent period or in healthy volunteers will be summarized separately.

9.4.8.1.3 Deaths, serious, and other significant adverse events

Any deaths, serious and other significant AEs will be listed.

9.4.8.1.4 Adverse events leading to treatment discontinuation

Any AEs leading to permanent treatment discontinuation will be listed.

9.4.8.1.5 Adverse events of special interest (AESI)

Number (%) of subjects experiencing treatment emergent AESI will be presented by AESI category and PT, sorted by decreasing incidence of PT within each AESI category.

9.4.8.2 Vital signs

Heart rate (HR), systolic and diastolic blood pressures (SBP and DBP), body temperature and respiratory rate will be analyzed as raw parameter value and change from baseline.

Body weight will be analyzed as raw parameter value and percent change from baseline. BMI will be analyzed as raw parameter value.

Baseline definition

The values to be used as baselines will be the D1 (V02, W0) predose assessment. If any of the scheduled baseline tests are repeated for any subject/patients, the last rechecked values will be considered as baselines, provided, for patients, they were done before the IMP administration of the respective treatment phase, and in the same condition.

Abnormalities analyses

For vital sign parameters, analysis will be performed using all post-baseline assessments done during the TEAE period/safety period, including all unplanned and rechecked values. Counts of subjects with Potentially Clinically Significant Abnormality (PCSAs) will be presented by cohort, regardless of the baseline status. PCSA values are defined as abnormal values considered medically important by the sponsor according to predefined criteria/thresholds based on literature review and defined by the sponsor.

A listing of individual data from subjects/patients with post-baseline PCSAs will be provided; values will be flagged when reaching the PCSA criteria.

Descriptive statistics and plots

For heart rate, blood pressures, body temperature and respiratory rate, raw data and absolute changes from baseline will be summarized in descriptive statistics (such as mean, median, SD, minimum, and maximum) for patients' cohort and scheduled time of measurement.

For body weight, raw data and percent change from baseline will be summarized in descriptive statistics (such as mean, median, SD, minimum, and maximum) by cohort and scheduled time of measurement.

9.5 INTERIM ANALYSES

A data quality control interim analysis for data quality purposes will be conducted after 10 patients are included and have completed the TEWL assessments at Day 1.

As it is an open-label study with no predefined hypothesis testing there is no issue regarding blinding or multiplicity adjustment.

The interim analysis will be performed using the safety population for safety parameters, the mITT and ITT populations for TEWL parameters. Only primary and secondary objectives for which data are available will be analyzed as described in Section 9.

9.6 DATA MONITORING COMMITTEE (DMC) OR OTHER REVIEW BOARD

No DMC or other review board is planned for this study.

10 SUPPORTING DOCUMENTATION AND OPERATIONAL CONSIDERATIONS

10.1 APPENDIX 1: REGULATORY, ETHICAL, AND STUDY OVERSIGHT CONSIDERATIONS

10.1.1 Regulatory and ethical considerations

- This study will be conducted in accordance with the protocol and with the following:
 - Consensus ethical principles derived from international guidelines including the Declaration of Helsinki and the applicable amendments and Council for International Organizations of Medical Sciences (CIOMS) International Ethical Guidelines
 - Applicable ICH Good Clinical Practice (GCP) Guidelines
 - Applicable laws and regulations (eg, data protection law as General Data Protection Regulation - GDPR)
- The protocol, protocol amendments, ICF, Investigator Brochure, and other relevant documents (eg, advertisements) must be submitted to an IRB/IEC by the Investigator and reviewed and approved by the IRB/IEC before the study is initiated.
- Any amendments to the protocol will require IRB/IEC approval before implementation of changes made to the study design, except for changes necessary to eliminate an immediate hazard to study participants.
- The Investigator will be responsible for the following:
 - Providing written summaries of the status of the study to the IRB/IEC annually or more frequently in accordance with the requirements, policies, and procedures established by the IRB/IEC Determining whether an incidental finding should be returned to a participant and, if it meets the appropriate criteria, to ensure the finding is returned (an incidental finding is a previously undiagnosed medical condition that is discovered unintentionally and is unrelated to the aims of the study for which the tests are being performed). The following should be considered when determining the return of an incidental finding:
 - The return of such information to the study participant (and/or his/her designated healthcare professional, if so designated by the participant) is consistent with all applicable national, state, or regional laws and regulations in the country where the study is being conducted, and
 - The finding reveals a substantial risk of a serious health condition or has reproductive importance, and has analytical validity, and has clinical validity.
 - The participant in a clinical study has the right to opt out of being notified by the Investigator of such incidental findings. In the event that the participant has opted out of being notified and the finding has consequences for other individuals, eg, the finding relates to a communicable disease, Investigators should seek independent ethical advice before determining next steps.

- In case the participant has decided to opt out, the Investigator must record in the site medical files that she/he does not want to know about such findings.
- Notifying the IRB/IEC of SAEs or other significant safety findings as required by IRB/IEC procedures
- Providing oversight of the conduct of the study at the site and adherence to requirements of 21 CFR, ICH guidelines, the IRB/IEC, European regulation 536/2014 for clinical studies (if applicable), and all other applicable local regulations

As applicable, according to Directive 2001/20/EC, the Sponsor will be responsible for obtaining approval from the Competent Authorities of the EU Member States and/or Ethics Committees, as appropriate, for any amendments to the clinical trial that are deemed as “substantial” (ie, changes which are likely to have a significant impact on the safety or physical or mental integrity of the clinical trial participants or on the scientific value of the trial) prior to their implementation.

